2.7.4 Other safety data

2.7.4.1 ECG and cardiac imaging data

12-lead ECG

PR, QRS, QT, QTcF, and RR intervals will be obtained from 12-lead ECGs for each participant during the study. ECG data will be read and interpreted centrally.

All ECG data will be listed by treatment group, participant and visit/time, abnormalities will be flagged. Summary statistics will be provided by study period, treatment group and visit/time.

In case multiple measurements on ECG are done for some visits. For numeric measurements, the mean of the scheduled measurements will be used. For ECG overall interpretation, most common interpretation (normal/abnormal) of the three assessments taken will be used. At visits with pre- and post-dose assessments, they will be presented separately.

A shift table from baseline to the worst post-baseline value will be presented based on the overall ECG interpretation.

Newly occurring observations of the number and percentage of participants with the following criteria will be summarized:

- QT Interval > 500 msec
- Absolute QTc (Fridericia's) interval > 450 msec (males), absolute QTc (Fridericia's) interval > 460 msec (females)

- QTc (Fridericia's) interval change from baseline > 30 msec to < 60 msec, \geq 60 msec
- PR Interval > 250 msec
- PR Interval > 250 msec and PR Interval increase from baseline > 25%
- QRS Duration > 110 msec, > 120 msec
- QRS Duration > 120 msec and QRS Duration increase from baseline > 25%

For by-visit summary tables, scheduled visits (including remapped visits following the assessment window in [Section 2.1.1.5](#)) will be considered in the analysis. Unscheduled visits will not be included.

For notable summary tables, all post-baseline visits including unscheduled visits will be considered in the analysis.

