8.4.2 Electrocardiogram (ECG)

Electrocardiograms (ECGs) must be recorded according to the ECG investigator manual. The preferred sequence of cardiovascular data collection during study visits is ECG collection first, followed by vital signs, and blood sampling. The Fridericia QT correction formula (QTcF) should be used for clinical decisions.

Triplicate 12-lead ECGs are to be collected approximately 2 minutes apart for central analysis with ECG machines supplied by the core laboratory. The mean QTcF value for each visit will be calculated from the triplicate ECGs for each participant. At weeks 2, 12 and 52 pre and post-dose assessments should be collected (refer to [Table 8-1](#)), post dose assessment should be measured 

██████████ and the mean QTcF value for each timepoint will be calculated from the triplicate ECGs for each participant.

All ECGs, including unscheduled safety ECGs with clinically relevant findings collected during the study needs to be transmitted to the central ECG laboratory for review.

A monitoring or review process should be in place for clinically significant ECG findings throughout the study and especially at baseline before administration of study treatment.

In the event that a clinically significant ECG abnormality is identified at the site (e.g., severe arrhythmia, conduction abnormality of QTcF > 450 ms (males)/ 460 ms (females)), a copy of the assessment is sent to the core laboratory for expedited review if applicable, and the ECG is repeated to confirm the diagnosis. If the participant is hemodynamically compromised, the investigator or a medically qualified person must initiate appropriate safety procedures without delay (for example cardioversion).

Additional, unscheduled, safety ECGs may be repeated at the discretion of the investigator at any time during the study as clinically indicated. For any ECGs with participant safety concerns, two additional ECGs must be performed to confirm the safety finding.

Clinically significant abnormalities must be recorded on the CRF as either medical history/current medical conditions or adverse events as appropriate.

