2.1 Data analysis general information

The statistical analysis will be performed by Novartis personnel, using SAS Version 9.4 or above.

Summary statistics for continuous variables will include N, mean, standard deviation, minimum, first quartile, median, third quartile, maximum.

Summary statistics for categorical variables will be presented in contingency tables and will include frequencies and percentages.

The p-values will be presented as one-sided with level of significance 2.5%. 95% confidence intervals will be displayed and will always be two-sided.

The primary analysis may be conducted when all participants have completed their Week 24 visit or discontinued early and when a minimum of 150 participants across both Phase 3 pivotal studies (A2301 and A2302) have completed the 52 week treatment period. Details are given in this document.

The final analysis will be performed based on the final database lock when all participants have completed the study or discontinued early.

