CTCAE grades based on lab results alone will be applied programmatically. Clinical assessments (in *italic* below) will not be considered. In case of missing baseline laboratory assessment, it will be assumed as normal. The number and percentage of participants with CTCAE grade newly occurring or worsening after baseline will be presented. A case is considered as newly occurring abnormality if the value is not notable or missing at baseline but is notable thereafter. A case is considered as worsening abnormality if the value is notable at baseline and at least one post-baseline value is worse than baseline.

Shift tables will be provided on CTCAE grades to compare baseline relative to the worst grade. These summaries will be split into hematology and chemistry and will be presented by study period and treatment group.

Table 2-15 CTCAE grades for laboratory parameters to be analyzed

CTCAE term	Laboratory assessment	Grade 1	Grade 2	Grade 3	Grade 4
Anemia	Hemoglobin (Hgb)	<LLN-10.0 g/dL	<10.0-8.0 g/dL	<8.0 g/dL	Life-threatening consequences
Platelet count decreased	Platelet	<LLN-75,000/mm	<75,000-50,000/mm ³	<50,000-25,000/mm ³	<25,000/mm ³
White blood cell decreased	White blood cell	<LLN-3000/mm ³	<3000-2000/mm ³	<2000-1000/mm ³	<1000/mm ³
Neutrophil count decreased	Neutrophils	<2000-1500/mm ³	<1500-1000/mm ³	<1000-500/mm ³	<500/mm ³
Lymphocyte count decreased	Lymphocytes	<1500-800/mm ³	<800-500/mm ³	<500-200/mm ³	<200/mm ³
INR increased	INR	>1.2 - 1.5	>1.5 - 2.5	>2.5	-
Creatinine increased	Serum creatinine	>ULN-1.5 x ULN	>1.5 - 3.0 x ULN	>3.0 - 6.0 x ULN	>6.0 x ULN
Creatinine kinase increased	Serum creatinine kinase	>ULN-2.5 x ULN	>2.5 - 5.0 x ULN	>5.0 - 10.0 x ULN	>10.0 x ULN
Blood bilirubin increased	Total bilirubin (TBL)	>ULN - 1.5 x ULN	>1.5 - 3.0 x ULN	>3.0 - 10.0 x ULN	>10.0 x ULN
GGT increased	Gamma-glutamyl transferase (GGT)	>ULN - 2.5 x ULN	>2.5 - 5.0 x ULN	>5.0 - 20.0 x ULN	>20.0 x ULN

Alanine aminotransferase increased	Alanine aminotransferase (ALT)	>ULN - 3.0 x ULN	>3.0 - 5.0 x ULN	>5.0 - 20.0 x ULN	>20.0 x ULN
Aspartate aminotransferase increased	Aspartate aminotransferase (AST)	>ULN - 3.0 x ULN	>3.0 - 5.0 x ULN	>5.0 - 20.0 x ULN	>20.0 x ULN
Alkaline phosphatase increased	Alkaline phosphatase (ALP)	>ULN - 2.5 x ULN	>2.5 - 5.0 x ULN	>5.0 - 20.0 x ULN	>20.0 x ULN
Total cholesterol increased	Total Cholesterol	>ULN – 7.75 mmol/L	>7.75 – 10.34 mmol/L	>10.34 – 12.92 mmol/L	>12.92 mmol/L

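### SAP 2.7.4.1 plans no count by treatment group of QTcF above 480 or 500 ms, so crossings of these levels are merged with smaller ones or, from a prolonged baseline, may be counted in no QTcF row

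*SAP*

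**What the plan says.** The ECG part of the SAP (2.7.4.1) introduces its table of notable values with "Newly occurring observations of the number and percentage of participants with the following criteria will be summarized". Three of the criteria concern QTcF:

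- one absolute level, by sex: "interval > 450 msec (males), absolute QTc" and so on to above 460 ms for women;
- a moderate rise: "interval change from baseline > 30 msec to < 60 msec";
- a rise of 60 ms or more.

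The only 500 ms criterion is "QT Interval > 500 msec", which is uncorrected QT. On visits, the section says: "For notable summary tables, all post-baseline visits including unscheduled visits will be considered in the analysis". The planned ECG shift table uses the overall normal/abnormal reading, not QTcF categories.

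Section 2.7.4.1 does not define *newly occurring*. SAP 2.7.3 does so for laboratory values: "newly occurring abnormality if the value is not notable or missing at baseline but is notable thereafter". That section also has a worsening category for laboratory values, which the ECG section does not repeat.

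Protocol 16.1 defines a notable QTc for this trial as above 450 ms (men) or 460 ms (women), or an increase of at least 60 ms. It requires every such ECG to be flagged by the central cardiologist and assessed by the investigator. Protocol 4.5 lists QT effects as a potential risk. It describes outliers in the first-in-human studies by a QTcF above 480 ms or an increase of 60 ms or more.

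**The concern.** Protocol 4.5 names QT prolongation as a risk to be watched, and the 24-week placebo control is there partly to give a background rate for safety findings. A reader of the study report will want to know how many participants per group passed 480 ms and 500 ms. The planned table cannot answer that for anyone. A crossing from a normal baseline is pooled with values just above 450/460 ms. A crossing from a prolonged baseline may be counted nowhere among the QTcF rows. Of the two outlier conditions in 4.5, the rise of 60 ms or more gets a count against placebo here and the level above 480 ms does not. What is at stake is the clarity of one safety table. Efficacy is not touched.

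**Working it through.** There is no planned figure to reproduce; the check applies the listed rows as rules.

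**Inputs.** The three QTcF rows come from SAP 2.7.4.1. The meaning of *newly occurring* (criterion not met, or missing, at baseline and met afterwards) is borrowed from SAP 2.7.3. No inclusion or exclusion criterion in Protocol 5.1 or 5.2 sets a numeric QTcF limit, so a baseline above 450/460 ms is possible. The documents do not say how common it is.

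**Step 1: planned rows applied to examples (baseline to post-baseline).**

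| Participant | Change (ms) | New > 450/460 | > 30 to < 60 | ≥ 60 |
|---|---|---|---|---|
| Man, 430 to 465 | +35 | yes | yes | no |
| Man, 430 to 485 | +55 | yes | yes | no |
| Man, 451 to 510 | +59 | no | yes | no |
| Man, 460 to 485 | +25 | no | no | no |
| Woman, 470 to 490 | +20 | no | no | no |
| Man, 480 to 505 | +25 | no | no | no |

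The first two men cannot be told apart, although only the second passed 480 ms. That result does not depend on the borrowed definition, because 430 ms is normal at baseline. The last three examples do depend on it: they enter no QTcF row.

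**Step 2: baselines that lead to no QTcF row (whole ms).**

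- Post-baseline 481 ms: baseline 451–480 (men), 461–480 (women).
- Post-baseline 485 ms: baseline 455–484 (men), 461–484 (women).
- Post-baseline 501 ms: baseline 471–500 (both sexes).

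The row for a rise of 60 ms or more is sure to catch a value above 480 ms when the baseline is 420 ms or less, since 480 − 420 = 60.

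**Step 3: can the uncorrected QT row stand in?** By Fridericia, QT = QTcF × (60/HR)^(1/3). QT therefore equals 500 ms at HR = 60 × (QTcF/500)^3:

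- QTcF 485: 60 × 0.970^3 = 54.8 bpm
- QTcF 490: 60 × 0.980^3 = 56.5 bpm
- QTcF 505: 60 × 1.010^3 = 61.8 bpm

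At higher heart rates QT is below 500 ms, so the row misses these values from 55, 57 and 62 bpm upward. A QTcF of 501 ms at 75 bpm is a QT of 465 ms.

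**Step 4: can the by-visit summaries stand in?** SAP 2.1 gives "minimum, first quartile, median, third quartile, maximum", so an extreme at a scheduled visit would show. But by-visit ECG tables leave out unscheduled visits, and a maximum does not say how many participants crossed a level. With 2:1 allocation and no drug effect, the highest of 450 values falls in the larger arm with probability 300/450 = 0.67, so maxima are not a fair comparison between arms.

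**Step 5: the two added rows.** The man going from 460 to 485 ms counts under > 480. The man going from 480 to 505 ms counts under > 480 and > 500, because 480 does not itself exceed 480. The men starting at 430 ms are now separated. Still in no QTcF row: a man going from 451 to 480 ms (+29) or from 481 to 500 ms (+19), and anyone who enters above 500 ms and rises by 30 ms or less.

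**The case against.** The strongest reply is that the SAP already meets the trial's own standard. Protocol 16.1 sets the notable-QTc definition, and SAP 2.7.4.1 carries over all of it and adds a row. Protocol 12.5.2 asks only for listings, flags and summary statistics. The 480 ms level in 4.5 describes earlier first-in-human Holter data and commits this trial to no table. All of this stands. A reader might infer that the SAP contradicts the protocol; it does not.

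The second reply is that nothing is lost. Under 16.1 the central cardiologist flags every ECG above 450/460 ms whatever the baseline, and the investigator must assess it. For a clinically significant ECG abnormality found at the site, Protocol 8.4.2 adds that "a copy of the assessment is sent to the core laboratory for expedited review if applicable", with a repeat ECG. All ECG data are listed by treatment group, participant and visit with abnormalities flagged, and clinically significant findings can reach the adverse event tables. This also stands: a reader might infer that such participants go unnoticed or that the data disappear, and the documents show otherwise. But adverse event counts rest on investigator judgement, and a listing leaves the reader to build the n (%) by hand.

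Third, the prolonged-baseline examples rest on a definition taken from the laboratory section. That is right. It is the natural reading, but it should be stated as a condition. The master analysis plan that the SAP cites and the table shells were not available either, so a tiered QTcF output planned there cannot be excluded.

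**Conclusion.** The point holds as a minor reporting gap. SAP 2.7.4.1 plans no count by treatment group of QTcF above 480 or 500 ms. For normal baselines this follows directly from the row list. For prolonged baselines, the result that a participant may enter no QTcF row is conditional on the 2.7.3 meaning of *newly occurring* and on a rise of 30 ms or less.

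The number affected is not in the documents and is likely to be small: the worst-case mean QTcF effect projected in Protocol 4.5 is 2.580 ms. Individual cases remain flagged, assessed and listed, so the gap is confined to the comparative count. The documents give no ground for reading this as a failure of participant protection or as evidence of a QT signal. A reader might also infer that two extra rows would capture all worsening from a prolonged baseline; Step 5 shows that they would not.

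**What to change.** In SAP 2.7.4.1, keep the existing rows and add two: newly occurring QTcF > 480 ms and newly occurring QTcF > 500 ms, both sexes, as n (%) by treatment group and study period, with unscheduled visits included as for the other notable tables. Add one sentence saying that *newly occurring* has the meaning given in 2.7.3.

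This reduces the gap for prolonged baselines without removing it. If the sponsor wants the remainder covered, a worsening category like the laboratory one would be the direct way.

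The cost is two table rows and a sentence, using centrally read QTcF already collected. No new data, protocol amendment or change to eligibility or conduct is needed.

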2.7.4.2 Vital signs

All vital signs data will be listed by treatment group, participant, and visit/time and if ranges are available, abnormalities (and relevant changes) will be flagged. Summary statistics will be provided by study period, treatment group and visit.

Analysis in vital sign measurement using descriptive summary statistics for the change from baseline for each post-baseline visit will be performed. Change from baseline will only be summarized for participants with both baseline and post-baseline values and will be calculated as:

$$\text{change from baseline} = \text{post-baseline value} - \text{baseline value}$$

The number and percentage of participants with newly occurring clinically notable vital signs changes from baseline will be presented. Clinically notable vital sign results are provided in [Table 2-18](#) below.

Table 2-18 Clinically notable changes in vital signs

Vital sign (unit)	Clinically notable criteria
Systolic blood pressure (mmHg)	< 90 mmHg \geq 140 mmHg
Diastolic blood pressure (mmHg)	< 60 mmHg \geq 90 mmHg
Pulse (bpm)	< 50 bpm $>$ 100 bpm

For by-visit summary tables, scheduled visits (including remapped visits following the assessment window in [Section 2.1.1.5](#)) will be considered in the analysis. Unscheduled visits will not be included.

For notable summary tables, all post-baseline visits including unscheduled visits will be considered in the analysis.

[REDACTED]

[REDACTED]

[REDACTED]

[REDACTED]

2.10 Patient-reported outcomes

At the primary analysis and the final analysis, the values from baseline to the end of study will be summarized for LOU064 25 mg and Placebo-LOU064 25 mg treatment groups.

[REDACTED]

[REDACTED]

• [REDACTED]

[REDACTED]

[REDACTED]

[REDACTED]

[REDACTED]

[REDACTED]

Dermatology Life Quality Index (DLQI)

[figure not shown]
For the following DLQI assessments, summary statistics will be presented by treatment group for the FAS.

[figure not shown]
[REDACTED]

[figure not shown]
- DLQI = 0-1: the proportion of participants achieving DLQI = 0-1 response [REDACTED].

[figure not shown]
Angioedema Activity Score (AAS)

For the following AAS assessments based on AAS eDiary, summary statistics will be presented by treatment group for the FAS. Please see [Section 2.5.2.1](#) for derivation of AAS7 score and AAS7 = 0 response.

2.13 Interim analysis

A primary analysis may be conducted when all participants have completed their Week 24 visit or discontinued early and when a minimum of 150 participants across both Phase 3 pivotal studies (A2301 and A2302) have completed the treatment period. The minimum of 150 participants reaching week 52 should enable analysis on a minimum of 100 participants exposed to remibrutinib for 52 weeks, considering the initial randomization to either the remibrutinib or the placebo arm (2:1). The results of the primary analysis will further inform decision-making for the remibrutinib development program. Formal testing of the primary endpoint and key secondary endpoints will only be performed at the primary analysis time point; thus, no adjustment for multiplicity is required.

After the primary analysis and/or after all participants entered the open-label treatment period, additional optional interim analyses may be conducted at the discretion of the Sponsor to

support potential Health Authority requests and interactions (these interim analyses are not expected to have any impact on the conduct or scientific integrity of the study). The decision to conduct optional interim analyses and the timing of these analyses will be documented in the Statistical Analysis Plan prior to the conduct of any interim analysis. These interim analyses will be performed and interpreted by members of the Novartis clinical team.

3 Sample size calculation

3.1 Primary endpoint(s)

In order to fulfill registration and ICH E1 requirements on the number of participants treated for 6 months and 12 months in the development program, a sample size of 300 participants in the active arm and 150 in the placebo arm is targeted. Hence, the total sample size is 450 randomized participants.

From an efficacy point of view, the sample size justification is based on UAS7 change from baseline (for scenario with one primary endpoint), ISS7 and HSS7 change from baseline (for scenario with co-primary endpoints) and achievement of $UAS7 \leq 6$ and $UAS7 = 0$ at Week 12. To avoid assigning an unnecessary large number of participants to placebo, participants will be randomized in a 2:1 ratio to remibrutinib 25 mg b.i.d. and placebo arms, respectively.

All calculations were performed with nQuery Advisor 8.4.1.0 and Ri386 4.0.2 softwares.

For scenario with UAS7 as the primary efficacy endpoint

UAS7 change from baseline at Week 12

Approximately 10% drop-out is expected at week 12, thus with 270 participants in the active arm and 135 participants in the placebo arm, this gives a nominal power of more than >99% to detect a difference between remibrutinib and placebo if the mean change of UAS7 from baseline to Week 12 is at least 10 in favor of remibrutinib, with common standard deviation of approximately 12 (based on the primary endpoint analysis of Phase 2b study (CLOU064A2201)), based on a t-test, assuming type I error 0.025 (one-sided).

For scenario with ISS7/HSS7 as the co-primary efficacy endpoints

ISS7 change from baseline at Week 12

Approximately 10% drop-out is expected at week 12, thus with 270 participants in the active arm and 135 participants in the placebo arm, this gives a nominal power of more than >99% to detect a difference between remibrutinib and placebo if the mean change of ISS7 from baseline to Week 12 is at least 4 in favor of remibrutinib, with common standard deviation of approximately 6 (based on the primary endpoint analysis of Phase 2b study (CLOU064A2201)), based on a t-test, assuming type I error 0.025 (one-sided).

HSS7 change from baseline at Week 12

Approximately 10% drop-out is expected at week 12, thus with 270 participants in the active arm and 135 participants in the placebo arm, this gives a nominal power of more than >99% to detect a difference between remibrutinib and placebo if the mean change of HSS7 from baseline to Week 12 is at least 4 in favor of remibrutinib, with common standard deviation of approximately 6 (based on the primary endpoint analysis of Phase 2b study (CLOU064A2201)), based on a t-test, assuming type I error 0.025 (one-sided).

With 300 participants in the active arm and 150 participants in the placebo arm randomized in this study, this gives a power of more than >90% to detect a difference between remibrutinib and placebo in both mean change of ISS7 and HSS7 from baseline to Week 12 when correlation

between endpoints is 0 (conservative assumption, as higher the correlation is, higher the power is).

3.2 Secondary endpoint(s)

Achievement of UAS7 = 0 at Week 12

Similarly, with approximately 10% drop-out at week 12, then with 270 participants in the active arm and 135 participants in the placebo arm, this gives a nominal power of more than >99% to detect a difference between remibrutinib and placebo arm assuming a proportion of complete response (UAS7=0) of 0.35 in the remibrutinib arm and of 0.10 in the placebo arm, based upon a 2-group continuity corrected χ^2 test with a 0.025 one-sided significance level.

Achievement of UAS7 \leq 6 at Week 12

Similarly, with approximately 10% drop-out at week 12, then with 270 participants in the active arm and 135 participants in the placebo arm, this gives a nominal power of more than >99% to detect a difference between remibrutinib and placebo arm assuming a proportion of disease activity control response (UAS7 \leq 6) of 0.53 in the remibrutinib arm and of 0.15 in the placebo arm, based upon a 2-group continuity corrected χ^2 test with a 0.025 one-sided significance level.

The primary and secondary endpoints analyses are planned to use the multiple testing strategy to control the family-wise error at $\alpha=0.025$ (one-sided). It is considered, however, this hierarchical approach could impact the sample size compared to the separate endpoint approach, which depends on how the recycled alpha will be used. In both scenarios, the “family-wise” power (power to reject all null hypotheses) is >90% when correlation between endpoints is 0 (Higher the correlation is, higher the power is).

4 Change to protocol specified analyses

No change.

5 Appendix

